9.0 Study Drug Exposure and Compliance

Study drug exposure and compliance will be summarized using the mean, standard deviation, minimum, median, and maximum. Exposure to study drug (total patient years) will be summarized by treatment group.

The number of injections received at each schedule time point will be summarized with number and percent for each treatment group.

Study Drug Exposure (in Days) during the induction period:

For subjects who discontinued from the Induction Study:

- Date of last dose of Induction Study drug – Date of first dose of Induction Study drug + 14 days

For subjects who completed the Induction Study:

- Date of first dose of Maintenance Study drug or date of first dose study drug in Study M14-347 – Date of first dose of Induction Study drug + 1 day,
Or
- Date of last dose of Induction Study drug + 14 – Date of first dose of Induction Study drug + 1 day, whichever is shorter.

The date of last dose of Induction Study drug is defined as the date of last study drug injection before the date of re-randomization into Maintenance Study. The date of first dose of Maintenance Study drug is defined as the date of first study drug injection on or after the date of re-randomization into Maintenance Study.

Study Drug Compliance:

Treatment compliance will be summarized for each treatment group in the ITT population. The treatment compliance is defined as the number of injections actually

taken by the subject divided by the number of injections planned to be taken by the subject during the induction period.

10.0 Efficacy Analysis

10.1 General Considerations

All statistical tests will be two-sided with the significance level of 0.05. Descriptive statistics will be provided. These include the number of observations, mean, standard deviation, minimum, median, and maximum for continuous variables; and number and percent for discrete variables. The analysis will be performed using SAS[®] (SAS Institute Inc., Cary, NC, USA).

10.2 Primary Efficacy Analyses

This section provides the details of the primary efficacy analysis for the Induction Study.

Co-Primary Efficacy Variables:

- Proportion of subjects who achieve clinical remission at Week 4 (CDAI < 150).
- Proportion of subjects with decrease in SES-CD > 50% from Baseline (or for a Baseline SES-CD of 4, at least a 2 point reduction from Baseline) at Week 12.

Analysis Data Set for the Primary Efficacy Analysis:

The primary efficacy analysis will use the ITT analysis data set.

Imputation Method Used for the Primary Efficacy Analysis:

Missing CDAI at Week 4 or SES-CD at Week 12 will be imputed using the non-responder imputation (NRI) approach.

Statistical Method of the Primary Efficacy Analysis:

The comparisons between treatment groups on the two co-primary efficacy variables will be performed using the Cochran-Mantel-Haenszel (CMH) adjusted for hs-CRP at Baseline (< 10 and ≥ 10 mg/L), prior infliximab use (or prior anti-TNF use for subjects randomized under original protocol), and Crohn's disease severity (CDAI ≤ 300 , > 300) at Baseline. A CMH based two-sided 95% confidence interval for the difference between treatment groups will be calculated. Breslow-Day test for homogeneity of odds ratios will be performed as well. An exact CMH test will be used to handle zero cells.

For Week 4 clinical remission (CDAI < 150), LOCF, OC and multiple imputation methods will be used as sensitivity analyses. For Week 12 endoscopic response, OC will be used as sensitivity analysis.

In addition, as sensitivity analyses, the logistic regression including treatment, the randomization stratification factors and additional clinically important factors such as corticosteroid use at Baseline, IMM use at Baseline, Baseline fecal calprotectin, Baseline SES-CD, and Region (US versus ex-US) will also be performed for the co-primary endpoints.

The co-primary endpoints will be tested prior to the ranked secondary endpoints.

10.3 Secondary Efficacy Analyses

For the analysis purpose, the secondary efficacy endpoints for the Induction Study are divided into two groups: (1) ranked secondary endpoints and (2) additional, non-ranked endpoints.

Ranked Secondary endpoints:

1. Proportion of subjects with sustained clinical remission (CDAI < 150) at both Weeks 4 and 12.

2. Proportion of subjects with CDAI < 150 at Week 4 and decrease in SES-CD > 50% from Baseline (or for a Baseline SES-CD of 4, at least a 2 point reduction from Baseline) at Week 12.
3. Proportion of subjects with clinical remission (CDAI < 150) at Week 12.
4. Proportion of subjects who discontinued corticosteroid use and achieved clinical remission (CDAI < 150) at Week 12 among subjects taking corticosteroids at Baseline.
5. Proportion of subjects with endoscopic remission (SES-CD \leq 4 and at least a 2 point reduction versus baseline and no subscore greater than 1 in any individual variable) at Week 12.
6. Change from Baseline in fecal calprotectin level at Week 4.
7. Proportion of subjects with hs-CRP < 5 mg/L and fecal calprotectin < 250 μ g/g at Week 4.
8. Proportion of subjects with CDAI < 150, hs-CRP < 5 mg/L, and fecal calprotectin < 250 μ g/g at Week 4.
9. Proportion of subjects with CDAI < 150, hs-CRP < 5 mg/L, SES-CD \leq 4 and at least a 2 point reduction versus baseline and no subscore greater than 1 in any individual variable, and fecal calprotectin < 250 μ g/g at Week 12.
10. Proportion of subjects who achieve an SES-CED \leq 2 at Week 12.
11. Proportion of subjects with clinical response (decrease in CDAI \geq 70 points from Baseline) at Week 4.
12. Proportion of subjects with clinical response (decrease in CDAI \geq 70 points from Baseline) at Week 12.
13. Proportion of subjects achieving response in IBDQ Bowel Symptom domain (increase of IBDQ bowel symptom domain score \geq 8) at Week 4.
14. Proportion of subjects achieving response in IBDQ Bowel Symptom domain (increase of IBDQ bowel symptom domain score \geq 8) at Week 12.

15. Proportion of subjects achieving response in IBDQ fatigue item (increase of IBDQ fatigue item score ≥ 1) at Week 12.

For these endpoints which are categorical variables, NRI method of imputation will be used for the missing values. LOCF will be used as a sensitivity analysis wherever applicable.

Both LOCF and OC analyses will be performed for continuous endpoints. The LOCF analysis is considered primary for inferential purposes. In addition, Mixed-Effect Model Repeated Measure (MMRM) will be applied as a sensitivity analysis, wherever appropriate, for the longitudinal continuous endpoints.

For endoscopy related endpoints, there will be no LOCF imputation as there is only one post-baseline endoscopy during Induction. Only OC will be used as a sensitivity analysis.

The difference in proportions of subjects between treatment groups will be analyzed using the two-sided Cochran-Mantel-Haenszel (CMH) test adjusted for hs-CRP at Baseline (< 10 and ≥ 10 mg/L), prior infliximab use (or prior anti-TNF use for subjects randomized under original protocol), and Crohn's disease severity (CDAI ≤ 300 , > 300) at Baseline. Additionally, the CMH-based two-sided 95% confidence interval (CI) for the difference in the proportions between the treatment groups will be calculated. An exact CMH test will be used to handle zero cells.

The difference in change from Baseline between treatment groups will be analyzed using an ANCOVA model including factors of treatment, hs-CRP at Baseline, prior infliximab use (or prior anti-TNF use for subjects randomized under original protocol), and Crohn's disease severity at Baseline, and Baseline values. Parameter estimates with 95% confidence interval and *P*-value will be provided.

All additional efficacy endpoints will be non-ranked.

- Proportion of subjects with clinical response (decrease CDAI ≥ 70 points from Baseline) at each scheduled visit in Induction Study.

- Proportion of subjects with enhanced clinical response (decrease CDAI ≥ 100 points from Baseline) at each scheduled visit in Induction Study.
- Proportion of subjects who discontinue corticosteroid use at each scheduled visit in Induction Study among subject taking corticosteroids at Baseline.
- Proportion of subjects who achieve a composite subtotal score of SFPS < 50 at Week 12 who had an SFPS ≥ 100 at Baseline.
- Proportion of subjects who achieve a composite subtotal score of SFPS < 50 at Week 4 who had an SFPS ≥ 100 at Baseline.
- Proportion of subjects who achieve SES-CD ≤ 3 and at least a 2 point reduction versus baseline and no subscore greater than 1 in any individual variable at Week 12.
- Proportion of subjects with SES-CD = 0 at Week 12.
- Change from Baseline in fecal calprotectin level at each scheduled visit in Induction Study.
- Change from Baseline in hs-CRP at each scheduled visit in Induction Study.
- Change in IBDQ total score and individual IBDQ domain scores (bowel, emotional, social, systemic) from Baseline at each scheduled visit in Induction Study.
- Proportion of subjects with Inflammatory Bowel Disease Questionnaire (IBDQ) response (increase ≥ 16 points from Baseline) at each scheduled visit in Induction Study.
- Proportion of subjects with IBDQ remission (IBDQ ≥ 170 points) at each scheduled visit in Induction Study.
- Proportion of subjects achieving response in IBDQ fatigue item (increase of IBDQ fatigue item score ≥ 1) at Week 4
- Change in WPAI from Baseline at each scheduled visit in Induction Study.
- Change in EQ-5D from Baseline at each scheduled visit in Induction Study.
- Change in CDAI from Baseline at each scheduled visit in Induction Study.
- Change in SFPS from Baseline at each scheduled visit in Induction Study.
- Change in Abdominal Pain Rating Scale score from Baseline at each scheduled visit in Induction Study.

- Change in Bristol Stool Chart score from Baseline at each scheduled visit in Induction Study.
- Proportion of subjects who achieve Bristol Stool Chart response at each scheduled visit in Induction Study.
- Proportion of subjects who achieve CDAI remission (CDAI < 150) at each visit in Induction Study.
- Proportion of subjects who achieve SFPS remission (SFPS < 50) at each scheduled visit in Induction Study.
- Change in each CDAI component subscore (number of liquid or very soft stools, abdominal pain rating, general well-being, CD related complications, anti-diarrhea use, abdominal mass, hematocrit, body weight) from Baseline at each scheduled visit in Induction Study.
- Time to clinical remission (CDAI < 150) in Induction Study.
- Time to clinical response (CR –70) in Induction Study.
- Time to all cause Hospitalization in Induction Study.
- Time to CD-related Hospitalization in Induction Study.
- Proportion of subjects with no draining fistulas at Week 12 among subjects with draining fistula at Baseline.
- Proportion of subjects in each treatment group with > 50% reduction from Baseline in the number of draining fistulas at Week 12 among subjects with draining fistula at Baseline.
- Resolution of extra-intestinal manifestations over time at each scheduled visit in Induction Study.
- Proportion of subjects with an SES-CD decrease of ≥ 3 points compared to Baseline at Week 12.
- Proportion of subjects who achieve symptomatic remission, defined as average daily stool frequency ≤ 2.8 (and not worse than baseline) and average daily abdominal pain ≤ 1.0 (and not worse than baseline), at each scheduled visit in Induction Study among subjects with Baseline SF ≥ 4.0 and/or AP ≥ 2.0 .
- Proportion of subjects who achieve symptomatic response, defined as average daily stool frequency at least 30% reduction from baseline and average daily abdominal pain not worse than baseline or average daily abdominal pain at

least 30% reduction from baseline and average daily stool frequency not worse than baseline, at each scheduled visit in Induction Study among subjects with Baseline SF ≥ 4.0 and/or AP ≥ 2.0 .

The non-ranked secondary efficacy endpoints will be analyzed similarly to the ranked secondary efficacy endpoints.

Events of hospitalization and surgery will be identified by review of serious adverse events (SAEs) according to the hospitalization adjudication charter. All-cause hospitalization is defined as SAEs resulting in admission to the hospital or prolongation of an existing hospitalization for any reason. CD-related hospitalizations are defined as hospital admissions or prolongation of an existing hospitalization due to AEs that are related to CD. *P* values from both Log-rank test and Cox proportional hazards model will be provided.

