4.3 Sample Size

The calculated Week 4 remission rate for higher dose regimen are based on the average of the PK-PD Linear model and E_{\max} model and is 56% $[(70\% [\text{Linear}] + 42\% [E_{\max}]) / 2]$ for infliximab naïve subjects and 45% $[(60\% [\text{Linear}] + 30\% [E_{\max}]) / 2]$ for infliximab experienced subjects. Assuming the ratio in the proposed study of infliximab naïve subjects versus infliximab experienced is 75% versus 25%, respectively, the weighted Week 4 remission rate will be approximately 50% for higher induction dose regimen. For the standard dose regimen, the Week 4 clinical remission rate will be approximately 30%. Subjects who meet all of the inclusion criteria and none of the exclusion criteria will be enrolled into the study and randomized in a 3:2 ratio at Baseline to receive a higher induction adalimumab regimen or standard induction adalimumab regimen during the double-blind period. A sample size of 500 (300 higher dose and 200 standard dose) will be adequate to detect at least a 20% treatment difference in clinical remission rates at Week 4 between the dosing regimens using Fisher's exact test with 99% power at a 0.05 two-sided significant level.

Since exposure/endoscopic relationships are not currently available for adalimumab, clinical remission will be based on PK/PD modeling which predicts an expected ~50% increase in the proportion of subjects with endoscopic response compared to the standard adalimumab induction regimen. The observed rate of endoscopic response (decrease > 50% SES-CD from Baseline [or for a Baseline SES-CD of 4, at least a 2 point reduction from Baseline]) in Study M05-769 was 44% at Week 12 with the currently approved dosing regimen. Thus, by extrapolation, the expected rate for the higher induction regimen is 66%. A sample size of 500 subjects (300 higher induction regimen and 200 standard induction regimen) will be adequate to detect at least a 22% treatment difference in endoscopic response (decrease > 50% SES-CD from Baseline [or for a Baseline SES-CD of 4, at least a 2 point reduction from Baseline]) rates at Week 12 between the dosing regimens using Fisher's exact test with approximately 99% power at a 0.05 two-sided significance level.

Since the clinical remission at Week 4 endpoint and the endoscopic response at Week 12 endpoint are likely not independent of each other, the power for the co-primary endpoints for the study is expected to be $> 98\%$.

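### Ranked endpoint 7 is the only ranked responder endpoint a subject can already meet at Baseline, and the planned CMH test does not adjust for that status

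*SAP*

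**What the plan says.** Induction SAP section 10.3 (and Protocol section 5.3.3.2) defines rank 7 as the "Proportion of subjects with hs-CRP < 5 mg/L and fecal calprotectin < 250" µg/g at Week 4. It requires no change from Baseline and is not limited to subjects with a raised marker at entry. Missing values count as failures, and the analysis set is ITT (section 5.1).

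The CMH test for proportions is adjusted for hs-CRP at Baseline (below 10 v 10 mg/L or more), prior infliximab use and CDAI (300 or less v above 300). On the level, section 10.1 says: "All statistical tests will be two-sided with the significance level of 0.05". Section 10.4 tests the ranked endpoints in fixed order, so a failure at rank 7 ends confirmatory testing of ranks 8 to 15.

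Protocol sections 5.2.1 and 5.2.2 set no minimum hs-CRP or fecal calprotectin. Low values are expected: hs-CRP below 10 mg/L is a randomization stratum (SAP section 5.2), and Baseline calprotectin of 250 µg/g or less is a prespecified subgroup (SAP section 10.5).

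Some non-ranked endpoints do carry a Baseline condition. One is the "Proportion of subjects who achieve a composite subtotal score of SFPS < 50 at Week 4 who had an SFPS" of at least 100 at Baseline; symptomatic remission is similarly limited to subjects with raised symptom scores.

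**The concern.** A subject whose hs-CRP and calprotectin are both below the cut-offs at entry, and still are at Week 4, is a success in either arm. That subject says little about which induction regimen lowers the markers, yet stays in the numerator and the denominator. The planned hs-CRP factor separates these subjects only in part: its cut is 10 rather than 5 mg/L, and calprotectin is not a factor.

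At stake is the power of a test that stands before eight further ranked endpoints. The reported rate also needs care, because it mixes subjects who reached the target with subjects who were never above it.

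**Working it through.** **1. The plan's own power.** Inputs, all from SAP section 4.3: "A sample size of 500 (300 higher dose and 200 standard dose"); for the higher regimen, "the weighted Week 4 remission rate will be approximately 50% for higher induction dose regimen"; for the standard regimen, "the Week 4 clinical remission rate will be approximately 30"%; endpoint 2 on the standard regimen "was 44% at Week 12 with the currently approved dosing regimen", against 66% expected. The stated claim for Week 4 remission is a difference detectable "between the dosing regimens using Fisher's exact test with 99% power at a 0.05 two-sided significant level". Exact Fisher power is 99.4% for 50% v 30% and 99.8% for 66% v 44%. The product under independence is 99.2%, consistent with the stated figure above 98%. These figures reproduce. The plan states no rates and no power for endpoint 7.

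**2. Is rank 7 the only one?**
- Ranks 1 to 4, 8 and 9 need CDAI below 150; entry CDAI is 220 to 450.
- Rank 5 needs a 2-point fall in SES-CD.
- Rank 10 needs SES-CD of 2 or less; entry is at least 6, or at least 4 for disease limited to the ileum.
- Ranks 11 to 15 are defined by a change from Baseline.
- Rank 6 is continuous, not a responder endpoint.

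Only rank 7 can be met at entry.

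**3. Effect on the difference.** Let f be the share meeting both cut-offs at Baseline and r the share of them still meeting both at Week 4, taken as equal in the two arms. In each arm

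p(ITT) = (1 − f) × p(others) + f × r,

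so the ITT difference is (1 − f) times the difference among the others.

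**4. One case by hand (unstratified).** Assume 35% v 25% among the others, r = 80%, f = 20%.
- Higher: 0.8 × 0.35 + 0.2 × 0.8 = 0.44. Standard: 0.8 × 0.25 + 0.2 × 0.8 = 0.36. Difference: 0.08.
- Pooled rate: (300 × 0.44 + 200 × 0.36) / 500 = 0.408.
- SE under the null: √[0.408 × 0.592 × (1/300 + 1/200)] = 0.0449.
- SE under the alternative: √[0.44 × 0.56/300 + 0.36 × 0.64/200] = 0.0444.
- Power: Φ[(0.08 − 1.96 × 0.0449)/0.0444] = Φ(−0.18), about 43%.

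The same formula at f = 0 gives about 66% for 35% v 25%, 96% for 35% v 20% and 99.7% for 45% v 25%.

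**5. The planned test against the planned test plus Baseline status.** These are simulated CMH tests with all three planned factors. Every already-normal subject falls in the hs-CRP below 10 mg/L stratum. A repeat run, with half of subjects in that stratum, a quarter infliximab-experienced and half with CDAI above 300, agreed to within about 2 points. All rates, f and r are assumptions.

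| Others, higher v standard | r | f | ITT difference (points) | Power, planned strata | Power, Baseline status added |
|---|---|---|---|---|---|
| 35% v 25% | 80% | 10% | 9.0 | 55% | 58% |
| 35% v 25% | 80% | 20% | 8.0 | 44% | 49% |
| 35% v 20% | 85% | 10% | 13.5 | 89% | 92% |
| 35% v 20% | 85% | 20% | 12.0 | 79% | 85% |
| 45% v 25% | 80% | 10% | 18.0 | 98% | 99% |
| 45% v 25% | 80% | 20% | 16.0 | 95% | 97% |

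The added stratum gains about 1 to 6 points and never lowers power in these settings. At f = 20%, restricting the analysis to subjects abnormal at Baseline would reach about 57% in the first scenario and 91% in the second. That is more than the stratum recovers, but it answers a different question.

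**The case against.** The strongest reply is that endpoint 7 is a legitimate achieved-state endpoint: the proportion at target at Week 4. The SAP does not call it normalisation. Baseline-adjusted change in calprotectin at the same visit is already rank 6, analysed by ANCOVA. This stands, and it is why the endpoint definition need not change.

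A reader might infer that the plan limits its threshold endpoints to abnormal Baselines everywhere except here. It does not. SFPS below 50 at each scheduled visit and IBDQ of 170 or more are also unrestricted. The plan uses both conventions; rank 7 differs in being ranked and acting as a gate.

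A reader might also infer that rank 7 is badly underpowered because of dilution. The documents cannot show that. With 35% v 25%, power is only about 66% with no already-normal subjects at all, so much of that shortfall is the assumed effect. With a 20-point effect, the lower of the two differences in the plan's co-primary power calculations, the planned test keeps about 95% to 98%. Rank 7 is also reached only after both co-primaries and ranks 1 to 6 have succeeded, so unconditional power is not the chance that testing stops there.

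Finally, limiting the denominator is not the obvious remedy. It changes the estimand, departs from ITT and gives ranks 7 and 8 different populations, although rank 8 is rank 7 plus CDAI below 150.

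**Conclusion.** The point holds as a modest loss of efficiency. Rank 7 alone among the ranked responder endpoints can be met at entry, and the planned adjustment captures that status only through an hs-CRP cut at 10 mg/L. Already-normal subjects reduce the ITT difference by the factor (1 − f) and cost some power at the gate before ranks 8 to 15.

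The documents do not support a reading of bias or false-positive risk. Status at entry precedes randomization and is balanced in expectation, and under no treatment effect the test keeps its level.

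The size cannot be fixed from the documents. It rests on an assumed f of 10% to 20%, on assumed rates, and on equal persistence in both arms; if f is near zero the issue is negligible. Persistence also means being observed and not censored for corticosteroids, since such a subject otherwise counts as a failure. Within those assumptions, adjusting for Baseline status gains about 1 to 6 points of power.

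**What to change.** Keep endpoint 7 and its ITT denominator. In Induction SAP section 10.3, add Baseline marker status (hs-CRP below 5 mg/L and calprotectin below 250 µg/g at Baseline: yes or no, with missing counted as no) as a further CMH stratum for this endpoint only. Report the result among subjects with at least one marker at or above its cut-off at Baseline as a supportive analysis. Make the change before unblinding.

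No new data are needed: Protocol section 5.3.1.1 already uses the Screening hs-CRP and calprotectin as Baseline. The cost is a few sparser strata. The three planned factors give 2 × 2 × 2 = 8 cells. If the same Baseline hs-CRP is used throughout, only the four cells below 10 mg/L can split, so there are at most 12. Section 10.3 already provides an exact CMH test for zero cells.

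### Ranked endpoints 5 and 10 use fixed SES-CD cut-offs but are tested without Baseline SES-CD: about 0–2 power points lost at rank 5 under the planned effect, about 5–9 if the effect is half that

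*SAP*

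**What the plan says.** Induction SAP 10.3 lists "Proportion of subjects with endoscopic remission" at Week 12 as ranked endpoint 5 and SES-CD ≤ 2 at Week 12 as ranked endpoint 10. For all binary secondaries, "The difference in proportions of subjects between treatment groups will be analyzed using the two-sided Cochran-Mantel-Haenszel (CMH) test adjusted for hs-CRP at Baseline", together with prior infliximab (or anti-TNF) use and CDAI at or below versus above 300. Protocol 8.1.4.2 likewise adjusts categorical secondaries for the stratification variables only. The exact form of CMH is to be used where there are zero cells.

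Baseline SES-CD appears elsewhere:
- SAP 10.2 counts it among clinically important factors and puts it in a sensitivity logistic regression. That model is confined to the co-primaries: "Baseline fecal calprotectin, Baseline SES-CD, and Region (US versus ex-US) will also be performed for the co-primary" endpoints.
- SAP 10.5 splits it at the median for subgroup analyses, again of the co-primaries.
- For endoscopic secondaries, SAP 10.3 allows only an observed-case sensitivity analysis.
- Continuous secondaries are adjusted for their own baseline value by ANCOVA.

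SAP 10.4 tests the ranked endpoints in fixed order after both co-primaries. SAP 12.1 records no differences from the protocol.

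**The concern.** A fixed cut-off on a severity scale is easier to reach from a low starting score. None of the three CMH factors measures endoscopic severity. The SAP adjusts for Baseline SES-CD only for the co-primaries, where the endoscopic endpoint is already a change relative to baseline and adjustment matters least. It leaves the score out for the endpoints defined by an absolute level.

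Omitting a prognostic baseline value that every subject must have for entry costs power. It also leaves chance imbalance in starting severity uncorrected in the estimate. In a fixed sequence, a miss at rank 5 ends formal testing of ranks 6 to 15, which is ten endpoints.

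**Working it through.** **Inputs from the documents.** Test level: "All statistical tests will be two-sided with the significance level of 0.05" (SAP 10.1). Size: "A sample size of 500 subjects (300 higher induction regimen and 200 standard induction regimen") (SAP 4.3). Planned Week 12 endoscopic response is 44% versus 66%; planned Week 4 remission is 30% versus 50%. The only SES-CD ≤ 4 rates anywhere are 37% versus 55%, in the superseded text of Protocol Appendix N. I use them only as a planning range.

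**1. The plan's own power.** With n₁ = 300, n₂ = 200 and p̄ the pooled rate, power = Φ[(Δ − 1.96·√(p̄(1−p̄)(1/300 + 1/200))) / √(p₁(1−p₁)/300 + p₂(1−p₂)/200)].
- 66% v 44%: p̄ = 0.572; (0.22 − 1.96 × 0.0452)/0.0445 = 2.95; power 99.8% (Fisher exact 99.8%).
- 50% v 30%: p̄ = 0.42; (0.20 − 1.96 × 0.0451)/0.0434 = 2.57; power 99.5% (Fisher exact 99.4%).
- Both, under independence: 0.9939 × 0.9978 = 99.2%.

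The stated 99%, about 99% and > 98% are reproduced. The documents state no power for rank 5 or 10.

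**2. How the cut-offs depend on the starting score.**

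| Baseline | Drop needed for ≤ 4 | Drop needed for ≤ 2 | Co-primary |
|---|---|---|---|
| 6 | 2 (33%) | 4 (67%) | > 50% |
| 10 | 6 (60%) | 8 (80%) | > 50% |
| 20 | 16 (80%) | 18 (90%) | > 50% |

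Entry needs SES-CD ≥ 6, or ≥ 4 in ileum-only disease. Anyone starting at 6 or more who reaches 4 has already dropped 2 points, so the 2-point clause of rank 5 binds only for baselines of 4–5.

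**3. Cost at rank 5, with the association as a free parameter.** Simulation of 300:200 with a logistic outcome and 6,000 trials per row. Assumed: odds ratio per SD of Baseline SES-CD as shown, correlation 0.3 with the latent hs-CRP variable, a modest CDAI effect, 25% prior infliximab. Power is for the planned 8-stratum CMH, then with Baseline SES-CD added as a median split / tertiles.

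| Rates | OR per SD 0.61 | 0.37 | 0.22 |
|---|---|---|---|
| 37% v 55% | 98.1 → 98.1 / 98.1 | 97.9 → 98.9 / 98.9 | 97.6 → 99.2 / 99.4 |
| 27% v 40.5% | 87.6 → 88.5 / 88.5 | 87.5 → 90.7 / 91.2 | 88.4 → 93.1 / 93.5 |
| 30% v 42% | 78.6 → 79.2 / 78.6 | 78.0 → 81.6 / 81.8 | 79.1 → 86.3 / 88.0 |
| 25% v 35% | 66.7 → 66.8 / 66.6 | 66.6 → 70.5 / 70.7 | 67.1 → 75.1 / 76.0 |

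The gain is 0–2 points in the first row and 0–9 points over the whole range.

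**4. Cost with the association implied by the scale.** Here the Week 12 score is Baseline times a random remaining fraction.
- Calibrated to 44% standard-arm response with medians of 10–14, the implied odds ratio per SD was 0.15–0.53. Standard-arm rank 5 rates were 43–58% at or below the median against 8–29% above it. The weak case (0.61) did not arise.
- With medians of 10 and 13 and an effect near the planned 22 points, rank 5 power is already 97–99.8% and adjustment adds about 0–2 points.
- At about half that effect, the 16-stratum CMH adds 1–5 points. A standardised logistic model with continuous Baseline SES-CD adds 5–9. Type I error stays near 5%.

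**5. Zero cells with a fourth CMH factor.** The infliximab cap is 25% × 500 = 125 subjects. Spread evenly over 8 of 16 strata, that is about 15.6 each, of whom about 6 are on the standard regimen. At an above-median rate of 14%, such a cell has no responder with probability 0.86⁶ = 0.40. Over the four above-median cells, at least one is empty with probability 1 − 0.60⁴ = 0.87, before any other cell is counted. In simulation, at least one zero cell occurred at rank 5 in 97–100% of trials with 16 strata against 12–51% with 8. A second set of assumptions gave 82–100% against 6–47%.

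**The case against.** The strongest reply is that nothing is invalid. CMH on the randomisation factors holds its level, matches the design and follows the protocol. That stands. A reader might infer that the rank 5 and 10 tests are biased or that their error rate is inflated, and the documents do not support either reading.

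Second, a reader might infer a fixed loss, such as 3–8 power points whatever the effect. That is not supported either. Losses of that size need an effect well below plan, and at the only SES-CD ≤ 4 rates in the documents the loss is at most about 2 points. In the smaller-effect case the sequence may stop before rank 5: at 44% versus 55% response the co-primary itself has power Φ[(0.11 − 0.0895)/0.0454] = 67%, and ranks 1–4 must also succeed. This limits the practical gain. It does not remove it, because the 66% is an extrapolation and SAP 4.3 concedes that exposure–endoscopy relationships are not available.

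Third, rank 5 is not purely absolute, and the proportional-change model builds in baseline dependence. This stands in part. The 2-point clause rarely binds, but the subscore limit was not modelled, and the documents give neither the distribution of Baseline SES-CD nor its association with either endpoint.

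Fourth, the obvious one-line remedy, a median split as a fourth CMH factor, would make zero cells the norm. On a literal reading of the SAP the exact test would then become the usual analysis. With that rule applied, the gain under a weaker effect fell to between about −0.4 and +2.7 points. This stands, and it decides the form of the fix.

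**Conclusion.** The omission is real and affects efficiency only. Ranks 5 and 10 depend on the starting score, their tests leave it out, and no sensitivity analysis fills the gap. Under assumed Baseline SES-CD medians of 10–13 and proportional change, the cost at rank 5 is about 0–2 power points if 44% versus 66% response holds. It is about 5–9 points, against continuous-covariate adjustment, if the effect is about half that. Rank 10 shows similar or slightly smaller gains. These are marginal powers, given that testing reaches the endpoint. They rest on assumptions that the documents neither supply nor contradict. The change is worth making because the covariate is already collected and the benefit falls where the trial is least secure. The planned analysis remains usable without it.

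**What to change.** Before unblinding, amend Induction SAP 10.3 for ranked endpoints 5 and 10, and for the non-ranked SES-CD ≤ 3 and SES-CD = 0:
- Replace the CMH test with a logistic model containing treatment, the three randomisation factors and continuous Baseline SES-CD, for example on the log scale.
- Report the standardised risk difference with a robust 95% confidence interval. Fix the scale of the covariate and the variance estimator in the text, so that no choice remains after unblinding.
- Keep non-responder imputation, and keep the planned 8-stratum CMH as a sensitivity analysis.
- Do not add the median split as a fourth CMH factor.

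The co-primary analysis can stay as it is.

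Cost: a short SAP amendment using data already collected. It is a small departure from Protocol 8.1.4.2, so SAP 12.1 can no longer read as having no differences and must declare it. These endpoints will also be analysed by a different method from the other ranked proportions, which the report should explain.
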